#### 12.1 Sub-Study of Laboratory Outcomes:

The first approximately 62 to 82 patients will be analyzed as a sub-study to compare changes (from day 1 to days 5 and 10) in continuous laboratory outcomes between those on metformin to those on placebo (CRP, albumin, viral load, and microbiome changes (optional)), to help further understand mechanisms and apply for further funding early in the course of the trial. The study procedures are the same for those in the sub-study as the rest of the trial.

#### 12.2 Data Analysis:

A detailed SAP will be developed by the statisticians and included in the appendix prior to carrying out any unblinded data analysis of either cohort. Amendments to the SAP will be considered and developed by the blinded statistician(s). For secondary and tertiary outcomes, the unblinded statistician may participate in drafting amendments to the SAP but only for data for which their blind is not compromised. A brief analysis plan is outlined here. All analyses will

### UNIVERSITY OF MINNESOTA 08December2021 COVID-OUT (formerly called MET-COVID) (MET29324)

follow a modified intent to treat (mITT) principle, excluding participants who were postrandomization screen failures and who did not ingest any study drug. Formal comparisons will use 2-sided tests with a 5% significance level.

Descriptive statistics will be reported for baseline covariate information. Continuous variables will be summarized using mean and standard deviations, as well as median and interquartile range for skewed variables. Binary and categorical variables will be summarized using counts and percentages. Differences in important prognostic variables will be monitored visually with formal statistical testing undertaken only at the request of the DSMB.

Each study drug version control comparison will be separate. Each control group will consist of the participants who were eligible to receive the study drug but were assigned to a relevant placebo control arm instead. The metformin comparison will control for fluvoxamine and ivermectin use, and the fluvoxamine and ivermectin versus control comparisons will each control for metformin use. Primary hypotheses will be evaluated using logistic regression with a main effect for the relevant drug adjusted for study site and use of the other study drugs. The statistical significance of the main effect will be evaluated using a likelihood ratio test with interim monitoring boundaries specified above.

A secondary analysis for each study drug versus control comparison will control for age and BMI as well. Metformin effect heterogeneity with respect to biologic sex will be assessed in both cohorts though a logistic regression model with an interaction term, as well as separate logistic regression models fit to the data from males and females. During interim analyses, some participants will not have been followed adequately long for inclusion in the primary analysis. As a secondary analysis, marginal cumulative incidence rates in each arm at the specified follow-up interval will be estimated using the Kaplan-Meier method by censoring those in the midst of follow-up who have yet to experience the primary endpoint at their point of last study contact.

Laboratory outcomes, which are continuous longitudinally measured outcome, will be evaluated using generalized estimating equations with a treatment effect and adjustments for the corresponding outcome at baseline.

Secondary outcomes will be analyzed using generalized linear models with an appropriate distributional assumption and/or normalizing transformations. These analyses will adjust for study site and other prognostic information as appropriate. Time-to-event outcomes will be compared using Kaplan-Meier and log-rank tests as well as Cox proportional hazards models that adjust for prognostic variables. Ordinal endpoints will be analyzed using proportional odds regression models that adjust for prognostic variables and supplemented by logistic regression models for each ordinal threshold. These analyses will be supplemented by descriptive cumulative statistics for each ordinal category by treatment group. Detailed plans for primary, secondary and supplemental analyses will be provided in the SAP prior to conducting any unblinded data analyses.

All analyses will be carried out using R version 3.6.1 or newer.

12.3 Data Integrity:

The principal investigator will manage oversight of quality control for collected data. Recruitment of subjects will be performed using inclusion/exclusion criteria defined above Study data will be recorded within a REDCap database, which is HIPAA complaint, password protected with variable assignable security access and an audit trail consistent with all regulatory requirements for maintenance of clinical trial data. Data summaries and quality control checks will be run routinely.

12.4 Missing Data:

Research coordinators will make a consistent effort to ascertain all study data within the protocol specified windows, as well as outside these windows as needed. Participants who fail to respond will be contacted by study staff multiple times, and family will be contacted as well, prior to being recorded as lost to follow up. All data collected on a participant prior to loss to follow up or withdrawal of consent will be included in analyses. Missing values will be multiply imputed using chained equations and predictive mean matching via the mice package and the effect estimate and confidence intervals will reflect the uncertainty in these missing values. For the primary outcome variables, sensitivity analyses that are biased towards the null will be carried out by assuming missing outcomes in the placebo arm follow the estimated distribution in the treatment arm, and vice versa for missing outcomes in the treatment arm. Additional details will be provided in the SAP.

## 13.0 Safety

13.1 Adverse Event (AE)

At every study visit, participants will be asked a standard nonleading question to elicit any medically related changes in their well-being. They will also be asked if they have been hospitalized, had any accidents, used any new medications, or changed concomitant medication regimens (both prescription and OTC medications).

An AE is any symptom, sign, illness, or experience that develops or worsens in severity during the course of the study but does not necessarily have a causal relationship with study agent/intervention or procedures. Any medical condition that is present at the time that the participant is screened but does not deteriorate should not be reported as an AE. However, if it deteriorates at any time during the study, it should be recorded as an AE.

A clinical trial adverse event is defined as any untoward medical event associated with the use of a drug or study procedure. Non-serious adverse events will be collected during the period from enrollment (randomization) through the period on study drug, day 14. Any adverse event that is being collected as an expected Covid outcome by the Daily Covid Symptom Log or Clinical Outcomes assessments, or an expected side effect being collected by the Side Effect Survey, will only be recorded in those eCRF's and not additionally recorded in an adverse event eCRF. They will be reported to the DSMB at interim analyses.

Any adverse event that is not captured in the Covid Daily Symptom Log questions, Side Effect Survey, or Clinical Outcomes assessments will be recorded as an adverse event and reported to the DSMB at interim analyses. AE's will not be followed to resolution unless worsening during the course of the trial.

13.2 Serious Adverse Event (SAE)

Serious adverse events will be collected from enrollment through day 14 and 28. Investigators will determine if the event is serious or related to the study drug.

An SAE is any AE that is:

- Fatal,
- life-threatening,
- requires or prolongs a hospital stay,
- results in persistent or significant disability or incapacity,
- a congenital anomaly or birth defect, or
- an important medical event\*.

\*Important medical events are those that may not be immediately life threatening, but are clearly of major clinical significance. They may jeopardize the subject, and may require intervention to prevent 1 of the other serious outcomes noted above. For example, drug overdose or abuse, a seizure that did not result in in-patient hospitalization, or intensive treatment of bronchospasm in an emergency department would typically be considered serious.

SAEs must be entered into the study database within 24 hours of investigator awareness of the event.

13.3 Assessment of Safety

Scale used to Grade Severity of Adverse Events. Toxicity Grading Scale for Healthy Adult and Adolescent Volunteers Enrolled in Preventive Vaccine Clinical Trials https://www.fda.gov/media/73679/download). The scale provides a grading severity scale for AEs with unique clinical descriptions of severity based on this general guidance, and for this study an ED visit (without hospitalization) is considered Grade 3, not Grade 4 (a hospitalization is Grade 4).

13.4 Investigator Assessment of Serious Adverse Events

The Investigator will evaluate all SAEs with respect to **Seriousness** and **Causality** (relationship to study agent and relationship to research) as defined below.

13.5 Causality

The likelihood that the SAE is related to the study agent will be assessed by the investigator considering the following categorization. Due to the severity of COVID-19 illness further detailed breakdown will not occur:

- Definitely Related: There is clear evidence to suggest a causal relationship, and other possible contributing factors can be ruled out. The clinical event, including an abnormal laboratory test result, occurs in a plausible time relationship to study agent/intervention administration and cannot be explained by concurrent disease or other drugs or chemicals. The response to withdrawal of the study agent/intervention (de-challenge) should be clinically plausible. The event must be pharmacologically or phenomenologically definitive, with use of a satisfactory re-challenge procedure if necessary.
- Probably Related: There is evidence to suggest a causal relationship, and the influence of other factors is unlikely. The clinical event, including an abnormal laboratory test result, occurs within a reasonable time sequence to administration of the study agent/intervention, is unlikely to be attributed to concurrent disease or other drugs or chemicals, and follows a

clinically reasonable response on withdrawal (de-challenge). Re-challenge information is not required to fulfill this definition.

- Possibly Related: There is some evidence to suggest a causal relationship (e.g., the event occurred within a reasonable time after administration of the trial medication). However, the influence of other factors may have contributed to the event (e.g., the subject's clinical condition, other concomitant events). Although an adverse drug event may rate only as "possible" soon after discovery, it can be flagged as requiring more information and later be upgraded to probable or certain as appropriate.
- Unlikely: A clinical event, including an abnormal laboratory test result, whose temporal relationship to study agent/intervention administration makes a causal relationship improbable (e.g., the event did not occur within a reasonable time after administration of the trial medication) and in which other drugs or chemicals or underlying disease provides plausible explanations (e.g., the subject's clinical condition, other concomitant treatments).
- Not related: The AE is completely independent of study agent/intervention administration, and/or evidence exists that the event is definitely related to another etiology. There must be an alternative, definitive etiology documented by the clinician.
- 13.6 Investigator Reporting Responsibilities:
  - 13.6.1 Serious Adverse Events

All SAEs must be reported on the Serious Adverse Event case report form (SAE CRF) within 24 hours of awareness of the event. All other AEs must be reported within 5 business days of site awareness. The safety medical monitor will review all SAEs and determine the expectedness of each SAE.

13.6.2 Unanticipated Problems

An Unanticipated Problem is any event, incident, experience, or outcome that is

- unexpected in terms of nature, severity, or frequency in relation to
  - the research risks that are described in the IRB-approved research protocol and informed consent document; Package Insert, or other study documents;
  - the characteristics of the subject population being studied (persons with COVID-19); and
- possibly, probably, or definitely related to participation in the research; and
- places subjects or others at a greater risk of harm (including physical, psychological, economic, or social harm) than was previously known or recognized.

Unanticipated Problems will be reported in the study database. Unanticipated problems may include problems with protocol implementation, participant safety, and/or concerns regarding informed consent. Initial reports must be submitted within 7 calendar days of site awareness of the event.

13.7 Follow-Up of Serious Adverse Events

All unresolved SAEs will be followed by the CRC until the event is resolved or 14 days past the participants final study visit.

13.8 Sponsor's Reporting Responsibilities

Serious and unexpected suspected adverse reactions as defined in ICH E6 5.17 and as determined by the IND Sponsor will be reported to FDA, all participating country regulatory authorities, and all participating Investigators as IND Safety Reports.

The IND Sponsor will also submit an IND Annual Report of the progress of the investigation to the FDA and all participating country regulatory authorities.

## 14.0 Data Monitoring

14.1 Data Integrity Monitoring

Data entry will be performed by trained members of the research team who have received documented delegation of authority. Data integrity will be overseen by the PIs and the statistical team. A study monitor will review the electronic consent documents, study drug administration data, and SAE reporting. Additionally, a random sampling of subjects will undergo full evaluation and comparison of source documentation with data entered into the study database if source documentation is needed. Source documentation will be collected according to each institution's requirements for source documentation.

The first data monitoring visit will be scheduled within an appropriate time after the first subject is enrolled, with subsequent visits thereafter at designated time intervals. Monitors will evaluate study team members to ensure access is consistent with training and delegation of authority logs.

Sites will maintain binders (either paper or electronic) containing pertinent documents and information including IRB approval letters, documentation of GCP training, licenses, human subjects research ethics training certificates, curriculum vitae, and correspondence.

14.2 Data Safety Monitoring Board (DSMB)

A data safety monitoring board (DSMB) has been convened and includes individuals meeting the key element criteria below, it includes a biostatistician with prior clinical trials experience. The DSMB will follow the guidance as outlined in the application and the DSMB charter unless there is a compelling, unanticipated reason to deviate from these rules. Data regarding the primary outcome will be reported to the DSMB at weekly intervals or according to the frequency decided by the DSMB. The DSMB may recommend stopping the trial early only for safety, following these guidelines:

A. Patient Safety

A recommendation to suspend, alter the study, or stop for harm would occur if the lower bound for harm is crossed at any interim analysis for the primary efficacy outcome, or there is concerning evidence in the opinion of the DSMB, there is concerning evidence in the opinion of the DSMB that the rate of IRB-reported SAEs is higher in the experimental group than in the placebo group.

Despite the lower number of formal preplanned analyses, the DSMB will still receive near timely reports of hospitalizations and deaths, and can deviate from this strategy and

perform earlier testing if desired. They retain authority to change this plan if the reporting suggests harm prior to the first formal planned assessment if they feel that a formal hypothesis test is warranted.

B. Efficacy

Efficacy monitoring will be monitored in accordance to the guidelines in Section 12.4.2.

The DSMB will operate in accordance with guidelines established by the FDA in "Guidance for Clinical Trial Sponsors: Establishment and Operation of Clinical Trial Data Monitoring Committee" jointly published by the CBER, CDER and CDRH of the FDA (https://www.fda.gov/regulatory-information/search-fda-guidance-documents/establishment-and-operation-clinical-trial-data-monitoring-committees). The key elements include:

- 1. Expertise and independence: The members must have expertise in the area of study, not be study authors and have no financial conflict of interest.
- 2. Members will sign a confidentiality agreement.
- 3. It is preferred that the DSMB have a face-to-face initial meeting, but can meet by telephone thereafter more frequently.
- 4. All meetings must follow standard operating procedures (SOPs).

If the DSMB recommends closure of the study, then the DSMB Chair will email the principal investigator who will notify the IRB. If the trial is stopped for patient safety and a repairable cause of unacceptably high adverse events can be identified, the action must be reviewed and approved by the DSMB and IRB prior to resuming enrollment. For example, if one additional exclusion criterion is discovered that would account for the majority of unexpected events, this new exclusion criterion could be added, and the study could proceed.

#### 14.3 Data Security:

All standard confidentiality procedures will be observed for this study. Research staff will be trained on protocol and GCP standards before they will be allowed contact with participants or data. All data will be stored in a secure HIPAA compliant manner. No indefinable data will be stored on individual research computers or flash drives.

## **15.0** Provisions to Protect the Privacy Interests of Participants

15.1 Protecting Privacy:

Conversations will be held in a private room whenever possible. Telephone calls will be performed one on one. The electronic consent process will take place using a REDCap program that is secure and HIPAA compliant.

#### 15.2 Access to Participants:

Conduct of the study and determination of both safety and efficacy of the intervention requires access of the medical records. All study personnel undergo human subjects protection training and understand and value privacy standards set forth by HIPAA. Participants enrolled in the trial are made aware during the informed consent procedure that study personnel will be required to

access this private information for trial conduct, and consent to this access prior to agreeing to participate.

# **16.0** Compensation for Research-Related Injury

16.1 Compensation for Research-Related Injury:

The sponsor does not have funds for research-related injury compensation.

16.2 COVID-19 PREP Act

Due to the coronavirus public health crisis, the federal government has issued an order that may limit your ability to recover damages if you are injured or harmed while participating in this COVID-19 clinical study. If the order applies, it limits your ability to recover damages from the University, researchers, healthcare providers, study sponsor, manufacturer or distributor involved with the study. However, the federal government has a program that may provide compensation to you or your family if you experience serious physical injuries or death due to this study. To find out more about this "Countermeasures Injury Compensation Program" go to https://www.hrsa.gov/cicp/about/index.html or call [name].

## 17.0 Multi-Site Research

17.1 Study-Wide Number of Participants:

Up to 1,160 participants will be enrolled in the study to achieve the needed number of completed data sets.

17.2 Study-Wide Recruitment:

Each site will determine appropriate recruitment methods. A study brochure will be made available to all sites. Coordinators from the central site may help call positive patients at participating sites if a site becomes overwhelmed at any given time, given the rapidly changing geographic nature of this pandemic.

17.3 Communication with Sites:

All sites will be given access to study documents through the University of Minnesota BOX.

A project manager will be tasked with coordinate all communication, regulatory efforts, and ensuring sites are informed of study changes. The Project Manager will also work with the PI to ensure all non-compliance, adverse events, and other reportable events are reviewed and reported in accordance with local policies.

All study data will be entered into REDCap with each site being assigned a specific data access group so that staff at one site cannot see participant data from another site.

Personnel from all sites will participate in monthly progress meeting calls, which will include discussion of any problems including reportable events, interim results, and completion of the study. More frequent meetings may be planned, as necessary.

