### VERSION 3.4

\*Updated sample size: 225 per arm, 1,350 total.

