# Factorial design maximizes the use of placebo

Each patient gets 2 types of pills		Metformin (n=563)	Placebo (n=187)	
	Fluvoxamine (n = 375)	Metformin / Fluvoxamine n =188 6% event rate if both effective	Fluvoxamine / placebo n=187 11% event rate	
	Ivermectin (n=375)	Metformin/Ivermectin n = 188 6% event rate if both effective	Ivermectin/Placebo n = 187 11% event rate	
		Metformin / placebo n = 187 11% event rate	Placebo / Placebo n=187 20% event rate	
	Total	563	561	

[figure not shown]
• If two medications are effective, we will have 80% power to detect a difference over placebo.

• If only one medication is effective, we will have 90% power to detect a difference over placebo.

• Assumes a 10% loss to follow-up rate.

These considerations result in a planned enrollment of 1,124 participants (187-188 in each arm). Because these sample size calculations are based on marginal tests, the actual power may be higher when based on the planned tests using adjusted logistic regression models adjusted for various predictive factors as described later.

VERSION 3.4

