#### $H_0: \pi_T \ge \pi_C$ versus $H_A: \pi_T < \pi_C$

The hypothesized marginal rate of the primary endpoint under placebo is 20%. The expected event rate for the primary outcome in the single medication treatment arms is 11% which corresponds to a relative risk reduction of 45%. To detect this effect with 80% power using a marginal test with 5% two-sided type I error requires 337 participants in each comparison group. To account for effects of other drugs used in combination, which may reduce the event rate of the control group, for the interim analysis plan, and for losses to follow-up, we plan to enroll 1,124 participants in total.

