#### Prespecified analyses:

A detailed SAP will be submitted to the DSMB and updated if needed prior to analyses. The primary efficacy analysis for each study drug, metformin, fluvoxamine, and ivermectin, will be based on a logistic regression model with a main effect for the relevant drug controlling for study site, and use of the other study drugs. In particular, no interaction effects will be included in this analysis. Prespecified subgroup analyses

include: pregnant women, and individuals who have already received a SARS-CoV-2 vaccine.

The SAP includes a sample-size re-calculation procedure that was pre-specified for the analysis of futility and efficacy on the first 2/3 of participants enrolled. This procedure was presented to and approved by the DSMB at the DSMB analysis of futility and efficacy done after 2/3 of participants were enrolled, + 14 days of follow-up. The updated total sample size for the study based on this sample size re-calculation is 1,350. This re-estimation accounts for a larger portion of participants being vaccinated and greater prevalence of monocloncal antibody use after enrollment than was envisioned when the protocol was written in fall 2020, and the resultant impact on the event rate in the placebo control arm; and external evidence from the Together Trial indicating a 33% relative reduction from fluvoxamine for which the original sample size would not provide adequate power. The updated sample size is expected to provide 80% power to detect a 35% relative reduction from fluvoxamine, and similarly for ivermectin, while accounting for the recent impact of vaccination and therapeutics by using a projected estimate of the event rate for the primary outcome in the participants randomized to the placebo control arm.

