### UNIVERSITY OF MINNESOTA 08December2021 COVID-OUT (formerly called MET-COVID) (MET29324)

VERSION 3.4

Efficacy monitoring will be undertaken for each of the three active agents against its control. Efficacy monitoring boundaries will be based on a Kim and DeMets alphaspending function that mimics O'Brien-Fleming boundaries (parameter value of 3). This upper boundary controls one-sided type I error at 2.5%, and will be modified according to the information fractions at the time of the actual analyses (defined by the current evaluable sample size / maximum sample size). The monitoring boundaries that will be provided to the DSMB for each cohort are reported in Table 2 and updated based on the actual sample size(s) available at the time of each analysis. The lower futility boundary will be treated as non-binding and supplemented with conditional power calculations in conjunction with the DSMB. This futility boundary is based on a Kim and DeMets beta spending function with a parameter value of 1.5. The lower Haybittle-Peto boundary for harm of -2.5 with 50% or less of the planned enrollment and -2.0 otherwise will be considered binding, though harm will be assessed in conjunction with safety data and may be declared by the DSMB despite the primary efficacy endpoint analysis not achieving this lower boundary. (Monitoring boundary calculations have been and will be carried out using the gsDesign package in R version 3.6.1 or newer.)

Following the sample size re-estimation procedure, the upper efficacy boundary will be calculated by spending the remaining type I error rate in proportion to the specified Kim and DeMets alpha-spending function where the information fraction is calculated with respect to the updated sample size. This approach corrects for over-spending alpha relative to the revised sample size and controls the overall one-sided type I error rate at the intended 2.5% level (or equivalently the two-sided 5% level).

**Table 2:** Monitoring Boundary Guidelines on Z-Score Scale. The futility boundary will beconsidered non-binding and supplemented by conditional power calculations. The harm boundarywill be considered binding.

Sample Size	62	386	774	1,124
Efficacy	3.737	3.116	2.461	2.001
Futility	-2.130	-0.093	1.087	2.001
Harm	-2.500	-2.500	-2.000	-2.000

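### Section 17.1 still caps enrolment at 1,160, which is 190 below the updated total of 1,350

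*Protocol*

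**What the plan says.** The version history gives the updated sample size as the reason for version 3.4. The new total appears in two places: under the study overview in section 5.1, "Updated sample size: 225 per arm, 1,350 total", and in section 12.3.1 under the prespecified analyses, "The updated total sample size for the study based on this sample size re-calculation is 1,350". The second passage ties 1,350 to 80% power for a 35% relative reduction from fluvoxamine, and similarly for ivermectin.

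Section 17.1, which gives the study-wide number of participants, says instead: "Up to 1,160 participants will be enrolled in the study to achieve the needed number of completed data sets".

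The original design figure also remains. Section 12.3 has "These considerations result in a planned enrollment of 1,124 participants (187-188 in each arm" and section 12.3.1 has "we plan to enroll 1,124 participants in total". Table 2 in section 12.4.2 prints looks at 62, 386, 774 and 1,124. That section defines the information fraction as follows: "defined by the current evaluable sample size / maximum sample size".

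**The concern.** Section 17.1 is worded as an upper limit on enrolment, and 1,350 cannot be reached under a limit of 1,160. The figure counts people enrolled, so it cannot be explained as completers set against enrolled. Nor is it the original 1,124, so it cannot be read as a leftover statement of that design. A site, ethics board or monitor working from the multi-site section would find an authorised maximum below the number the trial now needs.

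If the limit were applied, the trial would close before reaching the size set by the re-estimation, and the power stated for the fluvoxamine and ivermectin comparisons would no longer apply.

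**Working it through.** **1. The discrepancy**

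Inputs: 1,160 (section 17.1); 1,350 and 225 per arm (sections 5.1 and 12.3.1); 1,124 (sections 12.3 and 12.3.1).

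- 6 × 225 = 1,350, so the updated total is consistent with itself.
- 1,350 − 1,160 = 190, and 190 / 1,350 = 14.1%.
- 1,160 / 6 = 193.3 per arm, against 225.
- 1,160 − 1,124 = 36.

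**2. What the shortfall could mean for power (illustration only)**

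The protocol does not print the projected control rate used in the re-estimation, so rates of 18%, 20% and 22% are assumed. Each fluvoxamine or ivermectin comparison sets two arms against two arms, so with full eligibility n = N/3 per group: 386.7 at N = 1,160 and 450 at N = 1,350. With a 35% reduction, pT = 0.65 pC. For a two-sided 5% test with no loss and no interim looks:

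power = Φ[(pC − pT − 1.96 s0) / s1], where s0 = √[2p̄(1 − p̄)/n], s1 = √{[pC(1 − pC) + pT(1 − pT)]/n} and p̄ = (pC + pT)/2.

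For pC = 0.20, pT = 0.13 and p̄ = 0.165:

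- N = 1,160: s0 = 0.02670, s1 = 0.02658; (0.0700 − 0.0523)/0.02658 = 0.665, so power is 74.7%.
- N = 1,350: s0 = 0.02475, s1 = 0.02464; (0.0700 − 0.0485)/0.02464 = 0.873, so power is 80.9%.

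| Assumed control rate | Power at 1,160 | Power at 1,350 |
|---|---|---|
| 18% | 69.3% | 75.8% |
| 20% | 74.7% | 80.9% |
| 22% | 79.4% | 85.1% |

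The gap is about 6 points throughout.

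**3. Where 1,160 probably comes from**

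Thirds of 1,160 are 386.7 and 773.3, close to Table 2's looks at 386 and 774. Thirds of 1,124 are 374.7 and 749.3. Using the stated spending function (Kim and DeMets, parameter 3, one-sided 2.5%), cumulative alpha is 0.025 t³ with t = n/maximum:

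| Maximum | t at 386 | t at 774 | Efficacy bound at 386 | Efficacy bound at 774 |
|---|---|---|---|---|
| Printed in Table 2 | – | – | 3.116 | 2.461 |
| 1,160 | 0.333 | 0.667 | 3.116 | 2.461 |
| 1,124 | 0.343 | 0.689 | 3.088 | 2.426 |
| 1,350 | 0.286 | 0.573 | 3.247 | 2.622 |

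With non-binding beta spending (parameter 1.5, beta 0.20), a maximum of 1,160 also returns the printed futility values −2.130, −0.093 and 1.087. A maximum of 1,124 gives −2.102, −0.040 and 1.158. The printed efficacy values at 62 (3.737) and at the end (2.001) match neither total: 1,160 gives 4.475 and 2.009, and 1,124 gives 4.455 and 2.013. The inference therefore rests on the looks at 386 and 774 and on the futility values.

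**4. Whether this affects the final test**

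The printed bounds 3.116 and 2.461, applied at 386 and 774, spend 0.0009 + 0.0065 = 0.0074 of the 0.025. Spending the remainder at 1,350 gives a final bound of 2.024, whichever maximum is named as their source.

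**The case against.** The strongest reply is that nobody would be misled. The version history, section 5.1 and section 12.3.1 all identify 1,350 as the updated size. Section 12.3.1 also contrasts it with the original one and records the monitoring board's approval of the re-calculation procedure. On this view 17.1 is an administrative line that the amendment missed, and the chance of actually stopping at 1,160 is small. Much of this stands. A reader might infer that the protocol leaves open which total is current, but it does not, and the 1,124 figures can be recognised as the superseded design. What the reply does not rescue is 17.1 itself: nothing in it marks the figure as historical.

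Three other stronger readings are tempting and should not be drawn.

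- **Table 2 threatens the error rate or leaves the final bound uncertain.** The link to 1,160 is inferred, since the table prints 1,124. The values are guidelines to be updated to actual sample sizes, and the printed bounds are slightly stricter than those for 1,124. A different final bound (2.034) would need interim bounds of 3.088 and 2.426, which the protocol does not print.
- **The protocol calls 1,124 underpowered in general.** Its remark, "relative reduction from fluvoxamine for which the original sample size would not provide adequate power", refers to a 33% relative reduction seen in an external trial.
- **The illustration shows that 1,350 misses its target.** It falls below 80% at an assumed 18%, but the protocol's projected rate is not printed, so the stated 80% is not tested here.

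**Conclusion.** The point holds as an internal contradiction in a number the trial relies on. Section 17.1 sets a ceiling of 1,160 where the same version sets the total at 1,350, a shortfall of 190 participants or 14.1%. That size comes from the document alone and needs no assumption. The power cost of about 6 points is illustrative: it assumes control rates of 18% to 22%, full eligibility for the drug, no loss and a fixed-sample test.

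That 1,160 was an earlier design maximum is a well-supported inference from Table 2, but it has no consequence for type I error or for the final bound.

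**What to change.** Change the figure in section 17.1 to 1,350, or to a stated number above it if that section is meant to leave headroom over the target.

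As an optional tidy-up, label the 1,124 in sections 12.3 and 12.3.1 and in Table 2's last column as the original design. Add a note that the Table 2 values at 386 and 774 reproduce a maximum of 1,160, not the printed 1,124. Leave those looks and values as they are, because the alpha spent there feeds the re-spending described in section 12.4.2.

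The cost is wording only: one number, and a few labels if the tidy-up is done. If 1,350 is entered, no participants are added beyond those already planned, and no analysis or boundary changes.
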